### **11.7.3 Physical Examinations and Vital Signs**

A PE of all body systems and vital signs assessment will be performed at the Screening and Week -4 Visits (see [Table 3-1](#) and [Table 3-2](#)). At other visits, symptom-directed PEs and symptom-directed vital sign assessments can be performed at the discretion of the investigator or healthcare provider.

A PE includes a review of the following systems: head/neck/thyroid; eyes/ears/nose/throat; respiratory; cardiovascular; lymph nodes; abdomen; skin; musculoskeletal; and neurological. Breast, anorectal, and genital examinations will be performed when medically indicated. After screening, any clinically significant abnormal findings in PEs will be reported as AEs.

Vital signs include blood pressure (systolic and diastolic), temperature (oral), pulse rate, and respiration rate. These will be assessed following a 5-minute rest in the seated or supine position.

#### 11.7.4 Electrocardiograms

Standard 12-lead ECGs will be performed using a machine with printout according to the Schedule of Assessments (Table 3-1 and Table 3-2). A window of  $\pm 15$  minutes will be allowed around the nominal times for all postdose ECG assessments. Additional standard 12-lead ECGs will be performed at any other time if clinically indicated. The performance of all ECGs will adhere to the following guidelines:

- The subject will be instructed to rest in the supine position for at least 5 minutes before having an ECG performed.
- The ECG will be performed before any other procedures that may affect heart rate, such as blood draws.

The ECG traces will be manually read at the study site at the Screening and Safety Follow-up Visits. A printout of the ECG traces will be made for safety review by the investigator and maintained with source documentation. Clinically significant ECG abnormalities occurring during the study through the Safety Follow-up Visit will be recorded as AEs.

To ensure safety of the subjects, a qualified individual at the study site will make comparisons to baseline measurements. If the QTcF is increased by  $>45$  msec from the baseline or an absolute QTcF value is  $\geq 500$  msec for any scheduled ECG, 2 additional ECGs will be performed approximately 2 to 4 minutes apart to confirm the original measurement. If either of the QTcF values from these repeated ECGs remains above the threshold value ( $>45$  msec from baseline or  $\geq 500$  msec), a single ECG will be repeated at least hourly until QTcF values from 2 successive ECGs fall below the threshold value that triggered the repeat measurement.

If the QTcF value remains above the threshold value ( $>45$  msec from the average of the 3 predose values on Day 1 or  $\geq 500$  msec) on repeated measurement or is noted on  $>2$  occasions with no identified alternative etiology for the increased QTcF study drug, then discontinuation from study treatment may be required after discussion with the medical monitor.

Subjects who discontinue treatment for increased QTc should have their QTc monitored closely until it normalizes or returns to baseline.

#### 11.7.5 Contraception and Pregnancy

##### 11.7.5.1 Contraception

The effects of VX-661 monotherapy or in combination with ivacaftor on conception, pregnancy, and lactation in humans are not known. Neither VX-661 nor ivacaftor showed any genotoxic potential in a standard battery of in vitro (Ames test, Chinese hamster ovary cell chromosomal aberration) and in vivo (mouse micronucleus) studies. VX-661 and ivacaftor were each found to be nonteratogenic in reproductive toxicology studies in rats and rabbits. Subjects should follow the contraception requirements outlined in this study protocol. The effects of VX-661 monotherapy or in combination with ivacaftor on the PK of hormonal contraceptives are not known. Thus, hormonal contraception is not an acceptable method of contraception for female subjects though it is acceptable for the female partners of male subjects.

At this stage in the development of VX-661 in combination with ivacaftor, participation in this study requires a commitment from the research subject and his/her partner to use at least 1 effective method of birth control. Acceptable methods of contraception for participants of this study and their partners are listed below. Methods of contraception should be in successful use from signing of consent, approximately 28 days, before the first dose of study drug (unless otherwise noted), and until 90 days following the last dose of study drug.

**Contraception for the couple is waived for the following:**

- True abstinence for the subject, when this is in line with the preferred and usual lifestyle of the subject. Periodic abstinence (e.g., calendar, ovulation, symptothermal, and postovulation methods) and withdrawal are not acceptable methods of contraception.
- If the male is infertile (e.g., bilateral orchiectomy). Infertility may be documented through examination of a semen specimen or by demonstration of the absence of the vas deferens by ultrasound or medical record before the first dose of study drug.
- If the female is of non-childbearing potential, per the following:
  - Postmenopausal: spontaneous amenorrhea for at least 12 consecutive months and serum FSH level  $\geq 40$  mIU/mL at Screening
  - Documented hysterectomy or a bilateral oophorectomy/salpingo-oophorectomy
  - Has not achieved menarche (has not had her first menstrual period). Females who fall into this category are considered not to be of childbearing potential only as long as they have not had their first menstrual period. If a female achieves menarche during the study, she will need to provide consent for compliance (proper method of contraception or abstinence).
- NOTE: All other female subjects who have had their first menstrual period will be considered to be of childbearing potential.

**Acceptable contraceptive methods:**

Acceptable contraceptive methods for **male subjects** or **male partners** of female subjects include the following:

- Vasectomy 6 months or more previously, with a documented negative postvasectomy semen analysis for sperm
- Condom and spermicide
  - In countries where spermicide is not available, condom without spermicide will be considered acceptable.
  - Local regulations may require use of an additional acceptable method of contraception.

Acceptable contraceptive methods for **female subjects** include the following:

- Bilateral tubal ligation performed at least 6 months previously
- Continuous use of an intrauterine device (non-hormone-releasing) for at least 90 days before the first dose of study drug
- Barrier contraception (such as diaphragm, cervical cap, or female condom) and spermicide
  - In countries where spermicide is not available, barrier contraception without spermicide will be considered acceptable.
  - Local regulations may require use of an additional acceptable method of contraception.
- NOTE: Hormonal contraceptives will not be considered as an effective method; however, female subjects are not required to discontinue hormonal contraceptives.

Acceptable contraceptive methods for **female partners** of male subjects:

- Bilateral tubal ligation performed at least 6 months previously
- Continuous use of an intrauterine device for at least 90 days before the first dose of study drug
- Barrier contraception (such as diaphragm, cervical cap, or female condom) and spermicide
  - In countries where spermicide is not available, condom without spermicide will be considered acceptable.
  - Local regulations may require use of an additional acceptable method of contraception.
- Hormonal contraceptives, if successfully used for at least 60 days before the first dose of study drug

**Additional notes:**

- Acceptable methods of contraception listed above are examples. Local requirements may prohibit the use of some of these examples. Please contact the medical monitor with any questions.
- A female condom cannot be used with male condom (as a double method of contraception) due to risk of tearing.
- Male and female subjects who are not sexually active at the time of screening must agree to follow the contraceptive requirements of this study if they become sexually active with a partner of the opposite sex.
- If applicable, additional contraception requirements may need to be followed according to local regulations and/or requirements.

- Male subjects must not donate sperm after the first dose of study drug, throughout the study, and for 90 days following the last dose of study drug.
- Female subjects and female partners of male subjects should not plan to become pregnant during the study through 90 days following the last dose of study drug.
- Male subjects whose female partner becomes pregnant through well-documented in vitro fertilization (donated sperm) or banked sperm (collected before the subject received study drug) must be compliant with the contraception requirements. In this scenario, the male subject and his female partner must commit to using barrier methods of contraception (to ensure there is no exposure of the fetus to study drug) for the duration of the study and until 90 days after the last dose of study drug.
- Female subjects should not nurse a child from the start of study drug dosing through 90 days following the last dose of study drug.
- Unique situations that may not fall within the above specifications should be discussed with the medical monitor.

#### **11.7.5.2 Pregnancy**

Subjects will be counseled to inform the investigator of any pregnancy that occurs during study treatment and within 90 days after the last dose of study drug.

If a female subject or the female partner of a male subject becomes pregnant while participating in the study, study drug must be permanently discontinued immediately. For male subjects, study drug does not need to be permanently discontinued if the female partner's pregnancy resulted from donated sperm or sperm banked before study drug exposure ([Section 11.7.5.1](#)). The investigator must notify the medical monitor and Vertex GPS within 24 hours of the site's knowledge of the subject's (or partner's) pregnancy using the Pregnancy Information Collection Form.

If the subject is confirmed to be on study drug, the subject or partner will be followed until the end of the pregnancy and the infant will be followed for 1 year after the birth, provided informed consent is obtained. A separate ICF will be provided to explain these follow-up activities. Pregnancy itself does not constitute an AE.

#### **11.7.6 Pulse Oximetry**

Arterial oxygen saturation by pulse oximetry will be measured at visits noted in [Table 3-1](#) and [Table 3-2](#). This will be assessed following a 5-minute rest (seated or supine) and before study drug dosing. At visits when study drug is taken at the site, pulse oximetry will be collected before the morning dose. This is a noninvasive measure of oxygen delivery to the tissues and has been correlated with clinical status and lung function.

### 11.7.7 Liver Function Test Parameters

#### Liver Function Testing

Liver function testing (ALT, AST, GGT, ALP, direct bilirubin, and total bilirubin) must be performed as noted in [Table 3-2](#) for serum chemistry, while subjects are receiving study drug treatment and at the Safety Follow-up Visit. These blood samples should be processed and shipped immediately per the Laboratory Manual.

Subjects with new treatment-emergent ALT or AST elevations of  $>3 \times \text{ULN}$  and clinical symptoms must be followed closely, including repeat confirmatory testing performed by the central laboratory within 48 to 72 hours of the initial finding and subsequent close monitoring of ALT and AST levels, as clinically indicated. In addition, if ALT or AST is  $>5 \times \text{ULN}$ , repeat follow-up levels must be obtained within  $7 \pm 2$  days.

If a subject cannot return to the site for liver function testing, a local laboratory may be used. Elevations in LFTs at the local laboratory must be reported immediately to the medical monitor, and the subject must have the tests repeated and sent to the central laboratory as soon as possible (ideally within 48 to 72 hours).

#### Study Drug Interruption

Study drug administration **must be interrupted** immediately (prior to confirmatory testing), and the medical monitor must be notified, if any of the following criteria is met and confirmed with repeat testing:

- ALT or AST  $>8 \times \text{ULN}$
- ALT or AST  $>5 \times \text{ULN}$  for more than 2 weeks
- ALT or AST  $>3 \times \text{ULN}$ , in association with total bilirubin  $>2 \times \text{ULN}$  and/or clinical jaundice

A thorough investigation of potential causes should be conducted, and the subject should be followed closely for clinical progression.

If no convincing alternative etiology (e.g., acetaminophen use, viral hepatitis, or alcohol ingestion) for the elevated transaminases is identified, regardless of whether ALT or AST levels have improved, study treatment must be permanently discontinued if repeat testing within 48 to 72 hours confirms the initial elevation. Subjects in whom treatment is discontinued for elevated transaminases should have their transaminases monitored closely until levels normalize or return to baseline.

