**VX-661/ivacaftor combination therapy**

- Morning dose: 1 tablet of fixed-dose combination of VX-661 100 mg/ivacaftor 150 mg and 1 tablet of placebo visually matched to ivacaftor
- Evening dose: 1 tablet of ivacaftor 150 mg

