
## 9.5 Removal of Subjects

Subjects may withdraw from the study at any time at their own request. Subjects may be withdrawn from study drug treatment at any time at the discretion of the investigator or Vertex for safety, behavior, noncompliance with study procedures, or administrative reasons. If a subject has been withdrawn from study drug treatment, the subject should continue to be followed as outlined in [Section 8.1.5](#), provided the subject has not withdrawn consent.

If a subject does not return for a scheduled visit, reasonable effort will be made to contact the subject. In any circumstance, reasonable effort will be made to document subject outcome. The investigator will inquire about the reason for withdrawal, request that the subject return all unused investigational product(s), request that the subject return for a Safety Follow-up Visit, if applicable ([Section 8.1.4](#)), and follow up with the subject regarding any unresolved AEs.

If the subject withdraws consent, no further evaluations will be performed and no additional data will be collected. Vertex may retain and continue to use any data collected before such withdrawal of consent.

The investigator should inquire about the reason for withdrawal of consent.

Subjects must return all unused study drug and return for all scheduled visits.

A subject will be withdrawn from study treatment for any of the following reasons:

- A female subject or a female partner of a male subject has a confirmed pregnancy.
- A subject's treatment is unblinded by the investigator.

A subject may be withdrawn from study treatment after a discussion between the investigator and the medical monitor for any of the following reasons:

- A subject develops a medical condition that requires prolonged concomitant therapy with a prohibited medication or prolonged interruption of the study drug.

- A subject develops a life-threatening AE or a serious adverse event (SAE) that places him/her at immediate risk, and discontinuation of study treatment deemed necessary.
- A subject is noncompliant with study requirements.
- A subject has an increase in transaminases (ALT or AST) according to evaluations and management described in [Section 11.7.7](#).
- A subject has an increase in QTc according to evaluations and management described in [Section 11.7.4](#).
- A subject develops a cataract or lens opacity.

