### 10.5 Study Drug Interruption

If study drug dosing must be interrupted for more than 72 hours, the medical monitor must be notified. In these instances, study drug dosing may only resume after approval by the medical monitor. Specific instructions for interruption for elevated LFT levels and elevated QTc levels are provided in [Section 11.7.7](#) and [Section 11.7.4](#), respectively.

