#### Resumption of Study Drug

If an alternative, reversible cause of transaminase elevation has been identified, study drug may be resumed once transaminases return to baseline or are  $\leq 2 \times \text{ULN}$ , whichever is higher. Approval of the medical monitor is required before resumption of study drug. Upon resumption of study drug, transaminases should be assessed weekly for 4 weeks. If a protocol-defined transaminase elevation occurs within 4 weeks of rechallenge with the study drug (with confirmation of the initial elevation by repeat testing within 48 to 72 hours), then the study drug must be permanently discontinued, regardless of the presumed etiology.

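### The hepatic interruption rule in Protocol Section 11.7.7 requires stopping before the confirmatory test but makes stopping depend on that test

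*Protocol*

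**What the plan says.** The rule is in Protocol Section 11.7.7, under the Study Drug Interruption subheading. It makes interruption mandatory and immediate, then continues: "prior to confirmatory testing), and the medical monitor must be notified, if any of the following criteria is met and confirmed with repeat testing". Three criteria follow: ALT or AST above 8 x ULN; ALT or AST above 5 x ULN for more than 2 weeks; and ALT or AST above 3 x ULN together with total bilirubin above 2 x ULN and/or clinical jaundice.

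Later under the same subheading there is a separate rule for permanent discontinuation. Where no convincing alternative cause is found, "study treatment must be permanently discontinued if repeat testing within 48 to 72 hours confirms the initial elevation". Under Resumption of Study Drug, a new elevation within 4 weeks of rechallenge also leads to permanent discontinuation, "with confirmation of the initial elevation by repeat testing within 48 to 72 hours".

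The general interruption section, 10.5, gives no liver rule of its own: "Specific instructions for interruption for elevated LFT levels and elevated QTc levels are provided in" Sections 11.7.7 and 11.7.4 respectively. Section 9.5 lists among the possible reasons for withdrawal from treatment: "A subject has an increase in transaminases (ALT or AST) according to evaluations and management described in" Section 11.7.7.

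**The concern.** The parenthesis places the interruption before the repeat test. The closing clause makes the interruption conditional on the result of that test. The protocol sends sites to this one sentence to decide when dosing stops at its most serious liver thresholds, in a population that includes adolescents from age 12.

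One site may stop at the first qualifying result. Another may rely on the closing clause and keep dosing until a repeat comes back. The duty to notify the medical monitor sits under the same condition, so a site that waits could delay that as well. Monitors would have no clear standard for deciding which conduct is a deviation.

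**Working it through.** There is no stated figure to reproduce. The check is mainly textual, with a short count of doses.

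**1. The sentence on its own.** Call the first qualifying result T0 and the confirmatory result T1, with T1 after T0. The parenthesis requires interruption before T1. The closing clause creates the duty only once T1 has confirmed T0. Both cannot be met.

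**2. Is it resolved elsewhere?**
- Section 10.5 refers to 11.7.7 for elevated liver tests.
- Section 9.5 refers to 11.7.7 for transaminase increases.
- Section 10.4 allows the investigator to interrupt or stop all study drugs. That is a permission and does not say when stopping is required.
- SAP Section 9.4.1.5 and Appendix I summarise liver thresholds, including ALT or AST above 3 x ULN with bilirubin above 2 x ULN as a category of its own. They contain no dosing rule.

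**3. Which clause is out of place?** Suppose confirmation were needed for interruption. Every interrupted subject would then already have a confirmed elevation, so the confirmation condition for permanent discontinuation would add little beyond its time window, and the parenthesis would mean nothing. Suppose instead that the closing clause is removed. The section then runs in order: stop at T0, repeat at 48 to 72 hours, discontinue permanently if the repeat confirms and no alternative cause is found. The rechallenge rule also ties confirmation to permanent discontinuation. The closing clause is the one that does not fit.

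**4. Which criteria are affected?** The criterion of more than 5 x ULN for more than 2 weeks already needs serial values. The conflict therefore affects the other two.

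**5. Doses at stake if a site waits.** Inputs:
- Dosing every 12 hours (Section 10.2).
- In the combination arm only the morning dose contains VX-661 (Synopsis: "Evening dose: 1 tablet of ivacaftor 150 mg").
- Repeat testing at 48 to 72 hours (Section 11.7.7). Using this as the wait before interruption is an assumption; the protocol states no such wait.

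| Assumed wait | Dosing occasions | With VX-661 (combination arm) |
|---|---|---|
| 0 h (stop at first result) | 0 | 0 |
| 48 h | 48/12 = 4 | 48/24 = 2 |
| 72 h | 72/12 = 6 | 72/24 = 3 |
| each further 24 h | +24/12 = +2 | +24/24 = +1 |

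Laboratory turnaround is not stated, and the last row shows what it would add.

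A less natural reading gives a larger range. Under Liver Function Testing, the 48 to 72 hour repeat is required for ALT or AST above 3 x ULN with clinical symptoms ("repeat confirmatory testing performed by the central laboratory within 48 to 72 hours of the initial finding"), and a follow-up level at 7 ± 2 days is required above 5 x ULN. A site that took the latter as its confirmation would wait 5 to 9 days: 5 x 2 = 10 to 9 x 2 = 18 occasions, 5 to 9 of them with VX-661. The interruption subsection itself uses 48 to 72 hours, so 4 to 6 is the fair central range.

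**6. Doses lost if the first result later proves unconfirmed.** Planned occasions over the randomized period are 8 x 7 x 2 = 112. Missing 4 to 6 of them is 4/112 = 3.6% to 6/112 = 5.4%, plus turnaround.

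**The case against.** The strongest reply is that the intent can be recovered. The parenthesis has no purpose except to tell sites not to wait, and the rest of the section attaches confirmation to permanent discontinuation. The closing clause looks like a drafting remnant. The two courses are also not equally exposed: because Section 10.4 lets the investigator interrupt at any time, stopping at the first result is permitted on either reading, while waiting contradicts the requirement to act immediately. The dose count assumes a site that overrides that requirement, and the 10 to 18 range treats a follow-up sample as a confirmatory one.

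Much of this stands. The intended order can be inferred, the safe course is always open, and the dose figures are conditional exposures that should not be read as expected ones. The 10 to 18 range should carry little weight.

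It is also fair to say that resumption is not wholly uncovered. For interruptions longer than 72 hours, Section 10.5 already requires medical monitor approval before dosing resumes. A resumption sentence in 11.7.7 would therefore be a clarification.

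None of this makes the sentence workable. Permission to stop does not replace a clear duty to stop, and a mandatory liver safety rule should not rely on each site inferring which half of it to ignore.

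**Conclusion.** The concern holds. The interruption rule cannot be followed as written, and neither document supplies an alternative. The permanent discontinuation rule in the same section is coherent; the defect is confined to the trigger for interruption, and in practice to two of its three criteria.

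The size is about 4 to 6 further dosing occasions per affected subject, 2 to 3 with VX-661 in the combination arm, plus laboratory turnaround. This assumes that a site waits for a repeat in the 48 to 72 hour window. The documents give no rate for such elevations, so the number of subjects affected cannot be estimated from them.

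This is a matter of subject safety and consistent conduct. It has no bearing on power, type I error or the efficacy analysis. It should still be treated as a required correction, because it sits in a mandatory stopping rule and costs almost nothing to put right.

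**What to change.** In Section 11.7.7, Study Drug Interruption, delete the last five words of the quoted clause so that the condition ends at the word *met*. Interruption, and notification of the medical monitor, then follow the first qualifying result. Leave confirmation at 48 to 72 hours where it already works, as a condition for permanent discontinuation.

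Under Resumption of Study Drug, add one sentence for a first result that the repeat does not confirm, for example that dosing may resume with medical monitor approval. The present text covers a different case: "If an alternative, reversible cause of transaminase elevation has been identified, study drug may be resumed once transaminases return to baseline", or are at or below 2 x ULN, whichever is higher.

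An optional tidy-up is to note in Section 9.5 that discontinuation is mandatory when the permanent-discontinuation criteria of 11.7.7 are met. Section 9.5 already defers to that section, so this is not a second contradiction.

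The cost is a wording change by amendment and a letter to sites. The one downside is an occasional short interruption for a result that is not confirmed: 4 to 6 of 112 planned occasions (3.6% to 5.4%), plus turnaround.
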